13. APPENDIX 3: AMENDMENT HISTORY					

KEY STUDY CONTACTS

Chief Investigator	[name]; [contact] ; [name]; [name]	
Study Co-ordinator	[name]; [contact]; [name]; [name]	
Sponsor	[name], [name]; [name]	
Joint-sponsor(s)/co-sponsor(s)	N/A	
Funder(s)	NIHR – primary research funds	
	Healthy Stadia – in-kind delivery support funding	
	Bet Know More – in-kind delivery support funding	
	Beacon Counselling Trust – in-kind delivery support funding	
Key Protocol Contributors	[name]; [contact] ; [name]; [name]	
	[name]; [contact] ; [name]; [name]	
	[name]; [contact] ; [name]; [name].	
	[name]; [contact]; Statistician; Robertson Centre for Biostatistics, University of Glasgow; [name]	
	[name]; [contact] ; London School of Tropical Hygiene and Medicine; [name]. [name]	
	[name] [name]; School of Psychology, Bangor University, [name]; [name]	
	[name]; [contact] ; [name]	
Committees	University of Glasgow, College of Social Science Research Ethics Committee.	

STUDY SUMMARY

Study Title	Football Fans and Betting (FFAB): a feasibility study and randomised pilot trial of a group-based intervention to reduce gambling involvement among male football fans			
Internal ref. no. (or short title)	Football Fans and Betting (FFAB): a feasibility study and pilot trial			
Study Design	A mixed methods feasibility study and pilot randomised controlled parallel group trial			
Study Participants	Male football fans who are heavily engaged in gambling who want to reduce their gambling involvement and improve their health and wellbeing.			
Planned Size of Sample (if	Phase 1: 12 – 16			
applicable)	Phase 2: 30			
	Phase 3: 120			
Follow up duration (if applicable)	12 months			
Planned Study Period	24 months			
Research Question/Aim(s)	Overall Aims			
	i) To develop and incorporate insights about UK sport bettors' behaviours into the current version of the FFAB programme and thus refine it for initial delivery (Phase 1: refinement);			
	ii) To test the feasibility of delivering the FFAB programme within professional football clubs (Phase 2: feasibility);			
	iii) To pilot the delivery of the FFAB programme under research conditions, assess research procedures for a future randomised controlled trial of an optimised FFAB programme, and refine our logic model (Phase 3: pilot).			
	Phase 1. Refinement of FFAB for initial delivery RQ1. Is FFAB acceptable to the target population (men who are regular sports bettors who want to reduce their gambling involvement)? RQ2. What (if any) further adaptations are needed to enhance acceptability, usability and engagement with the FFAB programme and associated smartphone gambling diary in the professional football setting? RQ3. How can the football club setting be used to			

best effect in recruitment strategies to attract and recruit men to FFAB?

Objective Phase 2. Feasibility of FFAB

RQ4. To what extent does FFAB succeed in attracting and retaining the target population?

RQ5. To what extent do football clubs, coaches and participants find FFAB and the associated smartphone app acceptable, and what changes (if any) are required?

RQ6. How well is FFAB implemented by coaches and what changes are needed to optimise coach training to deliver the FFAB programme?

RQ7. To what extent can the smartphone app be used to assess men's engagement with the programme, self-reported money and time spent gambling and physical activity?

Phase 3. FFAB pilot and assessment of research procedures

RQ8. Are the research procedures acceptable to FFAB participants (men, coaches and clubs)?

RQ9. Is there evidence that delivery and acceptability of FFAB varies by features of the football club context, such as gambling sponsorship?

RQ10. Does FFAB have the potential to encourage male sports bettors to reduce their gambling involvement and improve wellbeing?

RQ11. What additional measures should be considered as primary and secondary outcomes to enable a robust evaluation of behaviour changes (e.g. gambling behaviours and attitudes), improvements in mental health and wellbeing (e.g. wellbeing, selfesteem, health-related quality of life), and changes in underlying theoretical constructs (social support, autonomy, competence)? RQ12. What are the optimum methods for follow-up data collection? RQ13. Are there other intended and unintended (positive or adverse) consequences?

RQ14. Is it feasible to collect data on the relevant costs and consequences associated with gambling and potential pathways between gambling and its associated costs and outcomes over the short and long term?

RQ15. Does the FFAB logic model need refinement? RQ16. Do the findings warrant a full scale randomised controlled trial of the FFAB programme?

FUNDING AND SUPPORT IN KIND

FUNDER(S)	FINANCIAL AND NON FINANCIALSUPPORT GIVEN
National Institute for Health Research	Research funding
Healthy Stadia European Healthy Stadia Network [name] UK [name]	In-kind delivery support funding
BetKnowMore Betknowmore UK [name] [name]	In-kind delivery support funding
Beacon Counselling Trust Head Office: [name] [name]	In-kind delivery support funding

ROLE OF STUDY SPONSOR AND FUNDER

The University of Glasgow will sponsor the study, providing the necessary insurance to indemnify the study. The sponsor will monitor the study commensurate with risk as required.

The NIHR will fund the study, providing the necessary resources to conduct the study. Beyond this function, the funder will exercise no influence or control over data analysis and interpretation, manuscript writing, or dissemination of results.

ROLES AND RESPONSIBILITIES OF STUDY MANAGEMENT COMMITEES/GROUPS & INDIVIDUALS Study Steering Groups

Two groups are involved in the co-ordination and management of this study. Complying with best practice, this project will be managed by a Project Management Committee (PMC) and overseen by an independent Study Steering Committee (SSC).

The PMC will comprise of members of the study Investigators, including [name], [name], [name], [name], [name], [name], [name] and

[name]. They will be responsible for overseeing all aspects of the project design and delivery and co-ordinating the work of other partners, such as Healthy Stadia, and the team at Northumbria responsible for designing and delivering the smartphone diary app. They will function as the executive committee responsible for all decisions to be made on the project. The PMC will meet face to face, on average, once every six weeks to review progress, make key decisions and agree any risk migration actions required. During Phases 1 and 2, they will supplement face to face meetings with video conference calls. There will also be a further core delivery team of [name], [name] and the research associate who will meet on a weekly basis to plan actions and review progress, referring to the PMC where necessary. The full project team will meet at key milestones to agree actions. These include, but are not limited to, project inception to establish actions for the full project; end of Phase 1 to share learning and agree steps for Phase 2; end of Phase 2 to further share learning and agree steps for Phase 3; and after 12 month data collection in Phase 3 to agree outputs and dissemination activity, and review outcomes in relation to progression criteria. Detailed notes of all meetings with action points will be produced and agreed, and the CI will be responsible for ensuring that these actions are taken. A detailed project timetable will be produced, with dependencies clearly marked and shared with the whole team and used to track progress against key milestones.

The independent SSC will function as the executive committee overseeing the project, ensuring that the research is ethical and robust and providing advice to the PMC where needed. Membership of this independent group will be voluntary, with no remuneration or formal arrangements made (beyond the terms of reference, which will be drafted and agreed by the group). For this project, the SSC will be asked to operate as a critical friend to the PMC and this will be reflected in their terms of reference. Independent membership will include the following: Chair: [name] [name], a specialist in public health and alcohol research; additional members: [name], an expert in trials; [name], a sociologist with expertise in gambling and football; [name], a statistician; [name], Executive Director of the Gambling Commission; and [name], CEO of Sporting Chance (a charity providing treatment and education to professional sports people for mental health issues, including gambling); and representing public and patients, [name], a recovering problem gambler who has been assisting with the preparation of this proposal. [name] and [name] will represent the study team and [name] will represent the University of Glasgow's sponsorship team. The SSC will meet on average every 6-12 months throughout the duration of the project, or as required, with the timing of meetings to reflect key milestones and decisions, for example prior to Phase 3 implementation to discuss learning from Phase 2 and agree actions.

PROTOCOL CONTRIBUTORS

The University of Glasgow will sponsor the study, providing the necessary insurance to indemnify the study. Beyond this function, the sponsor will exercise no influence or control over data analysis and interpretation, manuscript writing, or dissemination of results. The sponsor exerted no control or influence over the final research design.

The NIHR will fund the study, providing the necessary resources to conduct the study. Beyond this function, the funder will exercise no influence or control over data analysis and interpretation, manuscript writing, or dissemination of results. The funder exerted no direct control or influence over the final research design, but did administer the peer review process through which the final design was arrived at.

Service providers and those with lived experience of gambling harm have been involved in, and contributed to, every stage of the development of this protocol. Members of two counselling organisations are included as Investigators on the project: [name], Clinical Director of Beacon Counselling Trust, and [name], former problem gambler and founder of BetKnowMore, an organisation which specialises in peer-peer support. Another former problem gambler, [name], is also involved in the project and has been invited onto the Study Steering Committee. All three have provided input and feedback on every stage of the protocol development; from research design, recruitment strategies and target population, to co-development of the intervention with the research team. They have provided particular advice on programme content and delivery, and in the adaption of techniques for supporting problem gamblers for our specific population of heavily engaged male bettors.

[figure not shown]
KEY WORDS: Gambling harm, behaviour change, sports betting, football clubs, gender sensitisation.

STUDY FLOW CHART

Figure 1: Flow diagram of study design

STUDY PROTOCOL

Football Fans and Betting (FFAB): a feasibility study and randomised pilot trial of a group-based intervention to reduce gambling involvement among male football fans

1 BACKGROUND

This study addresses an urgent and growing public health problem: gambling among the high-risk population of male sports bettors. Sports betting is a particularly male dominated form of gambling and is a major and highly visible area of growth for the gambling industry. Between 2014/15 and 2017/18 the online sports betting sector grew from £456m to £2.4bn, with online football betting increasing from £160m to £1bn, rising by £340m in the last year alone [1]. One in six men have placed sports bets in the past year [2]. Gambling companies are now the primary sponsor of half of the English Premier Football clubs, with in-play betting being heavily advertised and marketed to sports fans. Global trends in football-related sports betting indicate this trajectory will be sustained. It is likely that the gambling industry considers sports betting a large, untapped market. In the run up to the 2018 football World Cup, there was a notable increase in international operators launching sportsbooks aimed at the UK market, signalling the strategic importance of the UK market to businesses.

Gambling is associated with a range of adverse consequences and harms, affecting the health and wellbeing of individuals, families, communities and society. These can have enduring consequences that can exacerbate existing inequalities [3]. Gambling behaviour exists on a spectrum ranging from those who gamble and experience no adverse consequences, to those who experience some difficulties, to those whose gambling behaviour is defined as problematic against a range of validated criteria (e.g. health problems including stress, depression and anxiety) [4, 5]. The health harms from gambling can be severe, including self-harm, suicidal ideation and suicide attempts [6,7]. Longitudinal research has shown that stasis in gambling behaviour is not the norm, with people moving along the gambling-harms spectrum [8]. In Britain, a follow-up study of regular gamblers showed that nearly 1 in 3 (29%) of those who had previously reported no adverse consequences from gambling saw an increase in their experience of harms when re-interviewed one year later [9].

The experience of gambling-related harms is associated with higher levels of engagement in gambling activities [2]. Those who gamble 49+ times a year (i.e. ~weekly or more) are at greatest risk of experiencing harms, with around 1:10 estimated to experience adverse consequences as a result of their gambling, versus 1:100 of those who do not gamble/gamble under this threshold [10].

This study will first refine and then assess the feasibility of providing an independent, theoretically-informed and systematic intervention to regular male sports bettors who would like to reduce their involvement in gambling in the context of improving health and wellbeing. The intervention consists of a 9-week, face-to-face group based programme that aims to engage men in reducing their gambling involvement. It will be delivered by fully trained community coaches at professional football club home stadia. Each session lasts 90 minutes and includes 'classroom based' education round gambling behaviour,

motivations and impacts, followed by group-based physical activity sessions. Each session will be designed to be highly interactive, using whole group discussions, games and small group working to allow men to support each other to practice and build skills in order to monitor and reduce the amount of money and time spent gambling. A purpose built smartphone app will allow the men to record time and money spent gambling, as well as their daily step count, in a diary like format.

The study population will be male regular sports bettors aged 18 – 44 who feel their gambling may be affecting their health, wellbeing or relationships *and* who would like to make positive steps to change their gambling behaviour.

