8.1 Assessment and management of risk

Risk/ Potential risks of the study. We are aware that gambling can be a sensitive topic, and that asking men to talk about their attitudes about it could involve bringing up issues of compulsive behaviour, mental health issues and financial problems, and could be distressing for some. Discussing gambling in a group context could encourage some participants to reflect on their own behaviour, and may generate feelings of shame or stigma, or prompt some to think they may have a gambling problem. Unanticipated outcomes could include participation in the study enabling a partner/family member to realize that the participant was involved in gambling, and precipitating rows/relationship breakup, or causing them to drink more to cope with the worry. For some, it could increase feelings of shame or guilt as the participant realizes the broader impact of their gambling on others, or the extent to which gambling has limited their range of engagement in other things. Non-gambling related outcomes could relate to sustaining an injury as a result of increased involvement in physical activity as a consequence of

taking part in FFAB. Throughout the project, we will explore the consequences of taking part in the study within all qualitative interviews with participants and coaches.

Risk management plan for risks of harm to participant./ others: The project team are aware of the potential for distress that could arise from discussing gambling. We have made use of the extensive experience within our team to mitigate it. Academic members of the team have experience in designing health-based interventions around sensitive topics (eg weight loss), while the gambling behaviour organisations have experience of dealing with issues related to gambling harms and mental health. We are confident that the co-development of the research, and its ongoing monitoring by these individuals and groups, will work to minimise risk and safeguard participants wellbeing.

To this end, we have built in safeguards at each step of participants' trajectory through the research.

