- During recruitment, to ensure that participants understand the research and what it involves, participants will be provided with an information sheet and consent form which clearly explains the aims of the project, and their role in it. From the outset, this will include the details of project partners Betknowmore and Beacon Counselling Trust, as well as details of other organisations, including GamCare, a national treatment provider who have specialist online forums, chatrooms and a 24 hour helpline phone number. Discussion and questions about the research will be encouraged, to ensure that clear communication is established with the researcher, allowing for informed consent to be given.
- Before and during the sessions themselves, researchers will explain to participants that they do not have to participate in discussions/ respond to questions if they do not want to, and that if they become uncomfortable at any time, they are free to stop participating/ leave the group. Researchers will also be sensitive to the impacts of discussions during the focus groups and will monitor participants for signs of distress throughout. Being mindful of the group context of discussions, they will take steps to pause it if they feel that a participant needs a break, or if they wish to end the session. Researchers will be vigilant for signs of any psychological, emotional or other issues that may arise at any point during the study, and will be prepared to signpost/ refer an individual to sources of support if necessary. While coaches will be trained to ensure participants exercise within their limits, and how to respond when any injuries occur, any injuries that are sustained during the physical activity component of the project will be reported by coaches to the research team, as an adverse/serious adverse event.
- Throughout and at the end of discussions, details of organisations who provide support for a range of issues related to gambling, mental health and other problems, will be made available for participants who might wish to discuss anything further. These will be listed on the Participant Information Sheet. At the end of the session, participants will be thanked for their input and reminded of this list of organisations.

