Risk management plan: We have identified a referral procedure for dealing with safeguarding issues. It has been guided by our CI partner, [name], Clinical Director of the Beacon Counselling Trust. As well as being a specialist gambling treatment provider,

the Trust is also one of the largest mental health support providers across the North West of England, engaging with over 3500 patients per year. [name] has advised on adapting the Trust's protocol for referrals to the current study. As such, should any participant disclose to any team member as experiencing psychological, health or emotional issues during the study, or be identified by a team member as experiencing them, they will be offered an immediate referral for initial assessment at Beacon. There, they will be seen by a trained professional, who will make an assessment of their needs and identify the most appropriate next steps. This may involve continued care from Beacon therapeutic staff, or a referral into another, more appropriate service, which would be facilitated by Beacon. This process would be carried out following a standard care pathway, and in collaboration with the individual concerned.

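### Section 8.1 anticipates psychological and relationship harms from taking part, but its only stated adverse-event reporting rule covers physical-activity injuries, which control men cannot incur during the trial

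*Protocol*

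**What the plan says.** Section 8.1 of the Protocol sets out what might go wrong for a man who takes part. It names distress, shame or stigma, guilt, and a partner or relative learning of the gambling, "precipitating rows/relationship breakup, or causing them to drink more to cope with the worry". It also names injury from increased physical activity.

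The same section then says how such things are handled:

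- **Injury:** "any injuries that are sustained during the physical activity component of the project will be reported by coaches to the research team", and the sentence goes on to class these as adverse or serious adverse events.
- **Distress seen by researchers:** they "will be prepared to signpost/ refer an individual to sources of support if necessary".
- **Disclosed or observed problems:** "should any participant disclose to any team member as experiencing psychological, health or emotional issues during the study", or be identified by the team as doing so, "they will be offered an immediate referral for initial assessment at Beacon".
- **Other consequences:** "we will explore the consequences of taking part in the study within all qualitative interviews with participants and coaches".

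The term adverse/serious adverse event occurs nowhere else in the Protocol. The schedule in Appendix 2 has no adverse-event row, and the required documents in Appendix 1 include no event form. Section 1 describes the severe end of gambling harm in general: "The health harms from gambling can be severe, including self-harm, suicidal ideation and suicide attempts".

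**The concern.** The list of anticipated harms and the event-reporting rule stand in one section and do not match. Of the harms that 8.1 foresees, injury alone has a stated route into an event record. If staff follow the text, a strain at walking football is reported, and the text does not say whether a suicide attempt disclosed to a team member is reported too.

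Three uses of the pilot depend on this. RQ13 asks about unintended consequences, including adverse ones. RQ16 asks whether a full trial is warranted. The Study Steering Committee is charged with seeing that the research is ethical, yet no rule brings a serious psychological event to its notice. An analysis plan cannot repair this later, because it can only tabulate what was recorded.

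**Working it through.** No formula applies. The check sets each kind of harm against its stated handling and then asks who can contribute an event.

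**1. Anticipated harm against stated handling (section 8.1)**

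| Harm anticipated | Stated action | Stated as an adverse/serious adverse event? |
|---|---|---|
| Injury in the physical activity sessions | Coaches report to the research team | Yes |
| Distress, shame, guilt | Signposting, or offered referral | Not stated |
| Relationship breakdown, heavier drinking | Explored in interviews; offered referral if a problem is disclosed or seen | Not stated |

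Self-harm and suicidality appear only in section 1, as harms of gambling in general. They would fall under the referral route in 8.1, again with no stated recording.

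**2. Who can contribute an event under the stated rule**

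Section 7.2.1 gives 120 men, 60 per arm. Section 5 has control men continue their usual activities and receive the programme only after the project ends. The reportable injury arises in sessions that they do not attend. So 60 of 120 men, half the sample, cannot contribute an event during the trial, and the reports cannot compare arms even for injury.

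**3. Whether another part of the Protocol closes the gap**

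- *Outcome scales (section 4.2).* WEMWBS, ONS wellbeing, self-esteem, social support, EQ-5D, ICECAP-A and selected DSM-5 items are planned, with the outcome questionnaire completed in both arms at baseline, 10 weeks, 6 months and 12 months. They can show average worsening. None is listed as a count of self-harm, suicide attempts or admissions, and a mean score does not identify an event.
- *Qualitative work.* The Phase 2 focus groups ask about unanticipated adverse outcomes (section 5). In Phase 3, section 4.2 describes focus groups with intervention men, exit interviews with non-completers, and interviews with coaches and club representatives. None of these is described as including control men.
- *Economic data (section 5).* The feasibility of capturing mental health service use is tested. This measures resource use and is not event reporting.

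Each source adds something. None records individual serious events, and the only ones that cover both arms are questionnaires without an event item.

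**The case against.** The strongest reply is that the injury sentence is one bullet among session safeguards. It sets the coaches' reporting line; it does not define adverse events or exclude other kinds. That stands. A reader might infer that a suicide attempt is excluded by rule, or that a count of zero psychological events is built in. The text supports neither: it is silent, and staff might record such events anyway. The supportable statement is that no route is given.

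A reader might also set section 1 directly against section 8.1 as a contradiction. That goes too far. Section 1 describes gambling in general, and section 7.1.2 excludes men who screen as problem gamblers, so such events should be uncommon. They cannot be dismissed, however. Section 7.1 targets men who feel that gambling may be affecting their health, wellbeing or relationships. Section 1 also reports that 29% of regular gamblers with no previous harm had more harm a year later, and follow-up here is 12 months. The firm mismatch lies within 8.1.

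It is also true that the Protocol plans no event table and makes no safety claim, so a misleading report of no serious events is only a possibility. A confidence bound on zero events would serve no planned analysis, and none is offered here. Nor do RQ13 and RQ16 rest on the injury reports alone, given the scales and interviews.

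The last objection shapes the remedy. Intervention men are seen at nine weekly sessions and in focus groups; control men complete questionnaires. A by-arm table of whatever staff happen to notice would lean towards an excess in the intervention arm. Logging the source of each report would show that bias without removing it.

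**Conclusion.** The point holds as a gap in recording. Section 8.1 foresees psychological and relationship harms from taking part, reports only physical-activity injuries as adverse or serious adverse events, and gives the rest signposting or referral with no stated entry in an event record. Its size is structural, not numerical: every non-injury harm named in 8.1 lacks a stated route, and half of the randomised men cannot contribute an event during the trial.

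This rests on two readings: that the single sentence on injuries is the whole of the event-reporting rule, and that no separate procedure, uncited in the Protocol, supplies a wider one. It does not imply that participants go without care, that psychological consequences are ignored, or that serious events are expected to be frequent. It should be corrected before Phase 3 recruitment, because events that were not recorded cannot be reliably recovered at analysis.

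**What to change.** Reconcile the list of anticipated harms, the injury-reporting sentence and the referral plan within section 8.1:

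- Widen the adverse/serious adverse event definition to cover serious psychological events (including self-harm or suicide attempt), death, hospital admission, and referrals made under the 8.1 risk management plan, for any randomised man.
- Log each event with date, arm and source of report, and report the log descriptively to the Study Steering Committee.
- Compare arms only on events obtained in the same way in both. One route is the same adverse-consequence item in the self-completed questionnaire already planned at 10 weeks, 6 months and 12 months.
- Show events noticed at sessions or by coaches separately, with a note that they come to light more easily in the intervention arm.
- Add an adverse-event row to Appendix 2.

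The cost is one definition, one log, one questionnaire item and one schedule row. The change concerns recording only and leaves the referral route as it is.
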